4.2 Primary Efficacy Endpoint

The average change in FEV1 and FEF25-75% measured by spirometry at baseline visit and again 6 weeks later as well the average change in R5, Area of Reactance (AX), and X5 between the two visits as measured by IOS.

4.3 Secondary Efficacy Endpoints

The number of protocol-defined asthma exacerbations requiring treatment with oral steroids between the two groups will be monitored. We will also track frequency of albuterol use for acute symptoms, number of emergency room visits and hospital admissions for acute asthma exacerbations between the two groups.

4.4 Safety Evaluations

Rates of adverse events, withdrawal, adherence to treatment, and frequency of exacerbations; and resting respiratory rate and room air oxygen saturations over the 6 week treatment period, between patients in each treatment group. As we are using an FDA-approved drug for age-appropriate population, and with approved dosages, we anticipate no major safety issues.

5 SUBJECT SELECTION

5.1 Study Population

Subjects with a diagnosis of asthma who meet all of the inclusion and none of the exclusion criteria will be eligible for participation in this study.

5.2 Subject Eligibility Criteria

5.2.1 Inclusion Criteria

1. Diagnosis of asthma by pediatrician or asthma specialist
2. Informed consent by parent or legal guardian
3. 6 years to 18 years of age at Screening Visit
4. Ability to comply with medication use, study visits and study procedures as judged by the site investigator
5. FEF25-75% < 65% of predicted as a marker for small airway disease

5.2.2 Exclusion Criteria

1. Acute wheezing at Screening visit or at Baseline visit
2. Acute intercurrent respiratory infection, defined as an increase in cough, wheezing, or respiratory rate with onset in 1 week preceding Screening visit or 3 weeks preceding Baseline visit
3. Oxygen saturation < 95% at Screening visit or at Baseline visit
4. Clinically significant upper airway obstruction as determined by the Site Investigator (e.g. severe laryngomalacia, markedly enlarged tonsils, significant snoring, diagnosed obstructive sleep apnea)
5. Severe gastroesophageal reflux, defined as persistent frequent emesis despite anti-reflux therapy
6. Physical findings that would compromise the safety of the subject or the quality of the study data as determined by site investigator
7. ICS use within 7 days of Baseline visit, systemic steroid use within 30 days of Baseline visit
8. CF, ILD, history of severe BPD or other underlying significant respiratory disease apart from asthma
9. Potential subjects who are pregnant may not enroll in the study

6 CONCURRENT MEDICATIONS

Subjects should be maintained on the same chronic medications throughout the entire study period, as medically feasible. Each patient will be provided with an albuterol sulfate HFA inhaler as well as a spacer to be used with that device to be used for acute symptoms. Patients will be directed to use this as opposed to other albuterol inhalers they might have during the duration of the study.

6.1 Allowed

All standard therapies are allowed except as in 6.2.

6.2 Prohibited

Other ICS or combination ICS/LABA therapies at any time during the study period are prohibited.

7 STUDY TREATMENTS

7.1 Method of Assigning Subjects to Treatment Groups

We will use a block randomization scheme to promote balance at the end of the study. Block randomization ensures that after each block of individuals are enrolled in the study (n individuals in total); an equal number of individuals will be assigned to each group (n/2 individuals in each group). We will use random block sizes of 8-12. Data about grouping will be kept by study coordinator in a secure, locked location in the clinic. A password protected electronic database will also be created to store patient data in which will be kept on an encrypted, password protected computer.

7.2 Test Formulation

Subjects will be randomized equally to receive HFA Flunisolide 80mcg (AEROSPAN Inhalation Aerosol, MEDA Pharmaceuticals, Somerset, NJ) 1 inhalation BID or HFA Flunisolide 80mcg 2 inhalations BID. All inhalations will be delivered using the built-in spacer device without any other attached devices, holding chambers, spacers, or masks. Patients will be fully instructed on how to administer the medication exactly according to manufacturer's specifications as discussed in the package insert.

7.2.1 Packaging and Labeling

As this is an open label study, patients will be given the device in standard packaging from MEDA Pharmaceuticals.

7.2.2 Handling/Dispensing

Study Test Drug will be distributed by MEDA Pharmaceuticals to the clinic site. Albuterol sulfate (PROAIR HFA, TEVA Respiratory, Inc, Sellersville, PA) will be dispensed to each patient at the time of enrollment.

7.2.3 Dosage/Dosage Regimen

Flunisolide HFA: Subjects will be instructed to administer Study Drug with one or two inhalations twice a day depending on the group per the manufacturer's specifications as discussed in the package insert.

Albuterol: In order to standardize each participant's rescue therapy for acute symptoms, each enrollee will be provided with albuterol sulfate for breakthrough symptoms.

7.2.4 Administration Instructions

Each study subject and family will be provided step-by-step instructions on how to properly administer their medication.

7.2.5 Storage

Study Drug and albuterol sulfate should be stored in the site pharmacy in a secure location at room temperature/humidity.

7.3 Study Medication Accountability

An accurate and current accounting of the dispensing and return of Study Drug for each subject will be maintained on an ongoing basis by a member of the study site staff. The number of doses of Study Drug dispensed and returned by the subject will be recorded. The study monitor will verify these documents throughout the course of the study.

7.4 Measures of Treatment Compliance

Parents of subjects will be asked to bring all used and unused Study Drug containers to each study visit. Albuterol use can be documented via changes in the counter.

8 STUDY PROCEDURES AND GUIDELINES

A Schedule of Events representing the required testing procedures to be performed for the duration of the study is diagrammed in Appendix 1.

Prior to conducting any study-related activities, written informed consent and the Health Insurance Portability and Accountability Act (HIPAA) authorization must be signed and dated by the subject's legal representative in accordance with site IRB requirements.

8.1 Overview of Evaluations and Visits

8.1.1 Screening Evaluation

At the Screening visit, eligibility for the visit will be determined by the investigator based on inclusion and exclusion criteria. All eligible subjects will undergo spirometry to ensure that baseline values fit the inclusion criteria.

8.1.2 Baseline Visit

Eligible patients may proceed to the Baseline visit (Visit 2) no sooner than the next day but no later than 56 days following the Screening visit. Specific procedures taken at this visit are listed below. If the 56 day window is exceeded, subjects must repeat the Screening visit prior to repeating the Baseline visit. Refer to section 12 for clarification regarding screen failure and re-screening.

8.1.3 Interim Visits

Enrolled subjects will return at 6 weeks as detailed below.

8.2 Clinical Assessments

8.2.1 Demographics

Demographic information (date of birth, gender, race, ethnicity) will be recorded at the Screening Visit.

8.2.2 Medical History

Relevant medical history, including history of current disease, other pertinent respiratory history, diagnosis through newborn screening, exposure to environmental tobacco smoke, and information regarding underlying diseases will be reviewed and recorded at the Screening Visit.

8.2.3 Concomitant Medications and Pulmonary Exacerbations

All concomitant medication and concurrent therapies will be documented at the Baseline visit. Dose, route, unit frequency of administration, and indication for administration and dates of medication will be captured. An interim history and chart review will be performed at each subsequent study visit, including interim hospitalizations for respiratory symptoms and interim courses of steroids (date, route, indication).

8.2.4 Physical Examination

A complete physical examination will be performed by a physician (either the investigator or a co-investigator) at the Screening visit. An abbreviated physical examination will be performed by a physician (either the investigator or co-investigator) at Visits 2 and 3. Qualified staff (MD, NP, RN) may complete the abbreviated physical exam at all other visits. New abnormal physical exam findings must be documented and will be followed by a physician or other qualified staff at the next scheduled visit.

8.2.5 Height and Weight

Weight and height will be recorded at each visit.

8.2.6 Vital Signs

Heart rate, respiratory rate, and blood pressure will be measured with the subject at rest at each study visit. Body temperature will also be obtained.

8.2.7 Oximetry

Oxygen saturation will be measured on room air with the subject at rest at each study visit.

8.2.8 Adverse Events

Occurrence of treatment emergent adverse events will be assessed throughout the study. Onset, duration, severity, outcome, treatment and relation to study treatment will be documented.

9 EVALUATIONS BY VISIT

9.1 Visit 1 (Screening) (Day -1 to -56)

1. Obtain written informed consent and HIPAA authorization
2. Assign the subject a unique subject identification number
3. Review medical history, including a history of asthma, diagnosis date, and prior treatments
4. Review concomitant medications
5. Record demographic data
6. Obtain Vital Signs (temperature, resting HR, respiratory rate, and blood pressure)
7. Measure oxygen saturation on room air (oximetry)
8. Perform spirometry (pre and post bronchodilator)
9. Perform physical examination (Investigator)
10. Review inclusion/exclusion criteria to determine eligibility for study drug (Investigator)
11. If patient is female and has had menarche, will perform urine pregnancy test in office to exclude pregnancy.

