MDI	Metered Dose Inhaler
PI	Principal Investigator
SAE	serious adverse experience

PROTOCOL SYNOPSIS

TITLE	Flunisolide HFA in Children with Small Airway Disease
FUNDING AGENCY	MEDA Pharmaceuticals
PRINCIPAL INVESTIGATORS	[name] University of Louisville Louisville, KY [name] University of Louisville Louisville, KY
PRINCIPAL INVESTIGATOR SPONSOR	MEDA Pharmaceuticals
DATA COORDINATING CENTER	University of Louisville Physicians – Pediatric Pulmonology (Academic Office)
NUMBER OF SITES	One
STUDY DESIGN	Prospective, randomized, parallel, open label study
OBJECTIVE	To assess whether there is a dose-related difference with flunisolide HFA in pediatric patients with small airway obstruction based on pulmonary function parameters specifically designed to measure changes in small airway function.
NUMBER OF SUBJECTS	50

SUBJECT ELIGIBILITY CRITERIA	
Inclusion Criteria:
 
1. Diagnosis of asthma by pediatrician or asthma specialist2. Informed consent by parent or legal guardian3. 6 years to 21 years of age at Screening Visit4. Ability to comply with medication use, study visits and study procedures as judged by the site investigator5. $\text{FEF}_{25-75\%} < 65\%$ of predicted as a marker for small airway disease 
Exclusion Criteria:
 
1. Acute wheezing at Screening visit or at Baseline visit2. Acute intercurrent respiratory infection, defined as an increase in cough, wheezing, or respiratory rate with onset in 1 week preceding Screening visit or 3 weeks preceding Baseline visit3. Oxygen saturation $< 94\%$ at Screening visit or at Baseline visit4. Clinically significant upper airway obstruction as determined by the Site Investigator (e.g. severe laryngomalacia, markedly enlarged tonsils, significant snoring, diagnosed obstructive sleep apnea)5. Severe gastroesophageal reflux, defined as persistent frequent emesis despite anti-reflux therapy6. Physical findings that would compromise the safety of the subject or the quality of the study data as determined by site investigator7. ICS use within 7 days of Baseline visit, systemic steroid use within 30 days of Baseline visit8. CF, ILD, history of severe BPD or other underlying significant respiratory disease apart from asthma9. Patients who are pregnant may not enroll in this study

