9.2 Visit 2 (Baseline) (Day 0)

Subjects who meet eligibility criteria at Visit 1 will be scheduled to return for Visit 2 no sooner than the next day but no later than 56 days following the Screening Visit. The following procedures will be completed:

1. Obtain standardized asthma control score from parent/legal guardian
2. Review current health status/medical history
3. Review concomitant medications
4. Obtain vital signs (temperature, heart rate, respiratory rate and blood pressure)

5. Measure oximetry
6. Measure height and weight
7. Perform abbreviated physical examination (Investigator)
8. Have patient perform IOS pre-bronchodilator
9. Have patient perform spirometry pre-bronchodilator
10. Have patient perform IOS post-bronchodilator
11. Have patient perform spirometry post-bronchodilator

If the subject meets all eligibility:

12. Randomize to flunisolide HFA 80mcg 1 puff BID or flunisolide HFA 80mcg 2 puffs BID
13. Dispense Study Drug and albuterol sulfate with holding chamber.
14. Review instructions for Study Drug administration
15. Schedule subject for Visit 3 (Week 6 ± 1 week)

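### The only listed pregnancy test is at Screening, 1 to 56 days before randomisation, so no test confirms the pregnancy exclusion when study drug is dispensed

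*Combined protocol and SAP*

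**What the plan says.** **The exclusion.** Exclusion criterion 9 in section 5.2.2 reads "Potential subjects who are pregnant may not enroll in the study". The synopsis has the same rule: "Patients who are pregnant may not enroll in this study". Neither names a visit, but the synopsis heads the Baseline visit as the point of enrolment and randomisation.

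**The test.** Under step 11 of section 9.1 (Screening), for females past menarche, staff "will perform urine pregnancy test in office to exclude pregnancy". No other visit list mentions a pregnancy test.

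**The interval.** Section 9.2 schedules Visit 2 "no sooner than the next day but no later than 56 days following the Screening Visit". Section 8.1.2 adds: "If the 56 day window is exceeded, subjects must repeat the Screening visit prior to repeating the Baseline visit".

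**The gate at Baseline.** Section 9.2 lists 11 procedures, then the condition "If the subject meets all eligibility", then randomisation (step 12) and dispensing (step 13). Section 11 treats anyone who fails eligibility at Baseline as a screen failure who is not randomised.

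**The concern.** Pregnancy status can change between Screening and Baseline, and so can menarche, which decides who is tested. The protocol evidently did not think history enough at Screening, because it asks for a urine test there. It gives no reason why history should be enough up to eight weeks later, at the visit where the exclusion takes effect and drug is handed out.

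What is at stake is whether a stated exclusion is carried out. A site that follows every listed step could give six weeks of study drug to a participant whom the protocol excludes, without departing from any listed procedure. Section 13 counts a failure to meet the entry criteria as a protocol violation, so the gap would surface only afterwards.

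**Working it through.** No sample size, power or alpha figure bears on this point. The check is day arithmetic on the visit window and a comparison of the visit lists.

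**1. Age of the test at randomisation**

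- Inputs: Visit 1 falls on Day -56 to Day -1 (heading of section 9.1); Visit 2 is Day 0 (heading of section 9.2).
- Formula: age of test = day of Visit 2 − day of Visit 1.
- Minimum: 0 − (−1) = 1 day.
- Maximum: 0 − (−56) = 56 days, and 56 / 7 = 8 weeks.
- Is 56 a true upper bound? Yes. Section 8.1.2 requires a new Screening visit, and therefore a new test, once the window is exceeded. Section 11 keeps a repeated Baseline visit inside the same window.

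The protocol gives no expected or typical interval, so only the range of 1 to 56 days can be stated.

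**2. What Visit 2 checks before step 12**

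| Section 9.2 steps | Content | Bears on pregnancy? |
|---|---|---|
| 1 | Asthma control score | No |
| 2 | Health status and history | Only through what is reported |
| 3 | Concomitant medications | No |
| 4 to 6 | Vital signs, oximetry, height and weight | No |
| 7 | Abbreviated examination | Not a test |
| 8 to 11 | IOS and spirometry, before and after bronchodilator | No |

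None of the 11 steps is a pregnancy test. Section 9.3 (Visit 3) has none either.

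**3. Who could pass through**

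The age range is 6 to 18 years in section 5.2.1 and 6 to 21 in the synopsis. Either range includes females past menarche and girls who may reach it during the window. Two routes lead to randomisation without a current test:

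- tested negative at Visit 1, conceived before Visit 2;
- not past menarche at Visit 1, so not tested there; past menarche by Visit 2, where no test is listed.

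The documents do not give the share of participants who are female or post-menarchal, or any pregnancy rate, so no expected number can be derived. With 50 participants and a window of at most 56 days, it is likely to be very small.

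**The case against.** **The criterion is applied at Baseline.** This is the strongest objection, and it limits the point. A reader might infer that pregnancy is not checked at all at Day 0. The documents do not support that: section 9.2 makes randomisation conditional on full eligibility, after a history review and an investigator's examination, and section 11 provides for failure at that visit. What is missing is confirmation by a test. That narrower statement stands, because the gate sets a condition without listing the means of checking this one that the protocol itself chose at Screening.

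**Appendix 1 may list a Baseline test.** Section 8 says that the schedule of events there shows the required testing. It was not in the text available for this review, so the possibility stays open. If it does list one, it disagrees with section 9.2 and the two need reconciling.

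**The interval may be shorter in practice.** The synopsis puts total participation at up to 8 weeks. Counted from Screening, that leaves 56 − 42 = 14 days before a six-week treatment period. This sits badly with the 56-day window in sections 8.1.2, 9.1, 9.2 and 11, and a test up to 14 days old would still not be a test at dispensing.

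**The drug is approved and used at approved doses.** True, as the synopsis and section 14 say. The protocol gives no rationale for the pregnancy exclusion and no pregnancy risk figure, and none is claimed here. The point is only that the exclusion and the procedures do not meet.

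**Other inferences that do not hold.**

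- A reader might infer that pregnancy was singled out because several other exclusions name the Baseline visit. Criteria 4, 5, 6 and 8 name no visit either, and enrolment is itself at Baseline.
- A reader might infer that repeating the Baseline visit lengthens the gap. Section 11 confines it to the same 56 days.
- A reader might infer a loss of power because withdrawn participants are not replaced (section 12.2). Section 13 leaves it to the principal investigator whether a violation leads to withdrawal, and section 12.1 encourages those who stop drug to complete their visits.
- The age of the test at Visit 3 is beside the point, because the exclusion governs enrolment.

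**Conclusion.** The point holds as a gap between an exclusion and the procedures that should deliver it. At randomisation and dispensing, the only listed pregnancy test is 1 to 56 days old, or was never done in a girl who reached menarche after Screening. Eligibility on this criterion then rests on history and an abbreviated examination.

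The practical size is small: few participants are likely to be affected, and there is no consequence for power, alpha or the primary comparison. It merits a change because an excluded participant could receive drug under exact adherence to the visit lists, and because closing the gap is cheap.

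The conclusion assumes that Appendix 1 adds no Baseline test and that enrolment means the Baseline visit, as the synopsis has it.

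**What to change.** Reconcile sections 5.2.2, 9.1 and 9.2, and Appendix 1, so that the exclusion is checked by the protocol's own office urine test at Visit 2, before step 12, in every female who has had menarche by that visit. Menarche status should be asked again at Visit 2, for instance within the history review at step 2. There are two ways to do it:

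- **Repeat the test.** Keep step 11 at Visit 1 as an early screen and add the same test to section 9.2. Suggested wording: *If the participant is female and past menarche at this visit, repeat the urine pregnancy test; proceed to randomisation only if it is negative.*
- **Move the test.** Transfer it from Visit 1 to Visit 2. This adds no test at a single Baseline visit, but a pregnancy present at Screening would be found only at Baseline.

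If it is repeated, the cost is one extra urine test per post-menarchal female per Baseline visit, at a visit already attended. As an illustration, if half of the 50 participants were female and all of those were post-menarchal, that would be 50 × 0.5 = 25 tests. The share is an assumption; between none and all, the range is 0 to 50 among those randomised. Participants who fail or repeat Baseline would add to the count. The other downside, under either option, is an occasional late screen failure.

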9.2 Visit 2 (Baseline) (Day 0)

Subjects who meet eligibility criteria at Visit 1 will be scheduled to return for Visit 2 no sooner than the next day but no later than 56 days following the Screening Visit. The following procedures will be completed:

1. Obtain standardized asthma control score from parent/legal guardian
2. Review current health status/medical history
3. Review concomitant medications
4. Obtain vital signs (temperature, heart rate, respiratory rate and blood pressure)

5. Measure oximetry
6. Measure height and weight
7. Perform abbreviated physical examination (Investigator)
8. Have patient perform IOS pre-bronchodilator
9. Have patient perform spirometry pre-bronchodilator
10. Have patient perform IOS post-bronchodilator
11. Have patient perform spirometry post-bronchodilator

If the subject meets all eligibility:

12. Randomize to flunisolide HFA 80mcg 1 puff BID or flunisolide HFA 80mcg 2 puffs BID
13. Dispense Study Drug and albuterol sulfate with holding chamber.
14. Review instructions for Study Drug administration
15. Schedule subject for Visit 3 (Week 6 ± 1 week)

9.3 Visit 3 (Week 6 ± 3 days)

1. Obtain standardized asthma control score from parent/legal guardian.
2. Review current health status/medical history and adverse events
3. Review concomitant medications.
4. Obtain vital signs (temperature, resting heart rate, respiratory rate and blood pressure)
5. Measure oximetry
6. Measure height and weight
7. Perform abbreviated physical examination
8. Have patient perform IOS pre-bronchodilator
9. Have patient perform spirometry pre-bronchodilator
10. Have patient perform IOS post-bronchodilator
11. Have patient perform spirometry post-bronchodilator

10 ADVERSE EXPERIENCE REPORTING AND DOCUMENTATION

10.1 Adverse Events

An adverse event (AE) is any untoward medical occurrence in a clinical investigation of a patient administered a pharmaceutical product and that does not necessarily have a causal relationship with the treatment. An AE is therefore any unfavorable and unintended sign, symptom or disease temporally associated with the administration of an investigational product, whether or not related to that investigational product.

The Investigator will probe, via discussion with the subject, for the occurrence of AEs during each subject visit and record the information in the site's source documents. Adverse events will be recorded in the subject CRF. Adverse events will be described by duration (start and stop dates and times), severity, outcome, treatment and relation to study medication, or if unrelated, the cause. Again, as this is an FDA approved medication being used in approved ages with approved dosages, we do not anticipate significant AEs.

AE Severity

The National Cancer Institute's Common Terminology Criteria for Adverse Events (CTCAE) Version 3.0, should be used to assess and grade AE severity, including laboratory abnormalities judged to be clinically significant. The modified criteria can be found in the study manual. If the experience is not covered in the modified criteria, the guidelines shown in 2 below should be used to grade severity. It should be pointed out that the term "severe" is a measure of intensity and that a severe AE is not necessarily serious.

Table 2. AE Severity Grading

Severity (Toxicity Grade)	Description
Mild (1)	Transient or mild discomfort; no limitation in activity; no medical intervention or therapy required. The subject may be aware of the sign or symptom but tolerates it reasonably well.
Moderate (2)	Mild to moderate limitation in activity, no or minimal medical intervention/therapy required.
Severe (3)	Marked limitation in activity, medical intervention/therapy required, hospitalizations possible.
Life-threatening (4)	The subject is at risk of death due to the adverse experience as it occurred. This does not refer to an experience that hypothetically might have caused death if it were more severe.

Table 3. AE Relationship to Study Drug Administration

Relationship to Study Drug Administration	Comment
Definitely	Previously known toxicity of agent; or an event that follows a reasonable temporal sequence from administration of the Study Drug ; that follows a known or expected response pattern to the Study Drug administration; that is confirmed by stopping or reducing the dosage of the Study Drug ; and that is not explained by any other reasonable hypothesis.
Probably	An event that follows a reasonable temporal sequence from administration of the Study Drug; that follows a known or expected response pattern to the administration of the Study Drug; that is confirmed by stopping or reducing the dosage of the Study Drug; and that is unlikely to be explained by the known characteristics of the subject's clinical state or by other interventions.
Possibly	An event that follows a reasonable temporal sequence from administration of the Study Drug; that follows a known or expected response pattern to administration of the Study Drug; but that could readily have been produced by a number of other factors.
Unrelated	An event that can be determined with certainty to have no relationship to administration of the Study Drug.

Table 4. AE Relationship to Pulmonary Function Testing (Spirometry/IOS)

Relationship to PFTs	Comment
Definitely	Previously known event that follows a reasonable temporal sequence from spirometry/IOS; that follows a known or expected response pattern to spirometry/IOS; that is confirmed by stopping spirometry/IOS; and that is not explained by any other reasonable hypothesis.

Probably	An event that follows a reasonable temporal sequence from the spirometry/IOS; that follows a known or expected response pattern to the spirometry/IOS; that is confirmed by stopping spirometry/IOS; and that is unlikely to be explained by the known characteristics of the subject's clinical state or by other interventions.
Possibly	An event that follows a reasonable temporal sequence from the spirometry/IOS; that follows a known or expected response pattern to the spirometry/IOS; but that could readily have been produced by a number of other factors.
Unrelated	An event that can be determined with certainty to have no relationship to the spirometry/IOS.

